### 3 Sample size calculation

### 4 Change to protocol specified analyses

NA

### 5 Appendix

#### 5.1 Imputation rules

##### 5.1.1 Study drug

No imputation will be made to the start and end date of study treatment.

##### 5.1.2 AE date imputation

No imputation will be made to the start and end date of AE.

##### 5.1.3 Concomitant medication date imputation

###### 5.1.3.1 CM start date imputation

The following table explains the notation used in the logic matrix. Please note that completely missing start dates will not be imputed.

	Day	Month	Year
Partial CMD Start Date	Not used	MON	YYYY
Treatment Start Date	Not used	TRTM	TRTY

The following matrix explains the logic behind the imputation.

	MON MISSING	MON < TRTM	MON = TRTM	MON > TRTM
YYYY MISSING	(1) Uncertain	(1) Uncertain	(1) Uncertain	(1) Uncertain
YYYY < TRTY	(2.a) Before Treatment Start	(2.b) Before Treatment Start	(2.b) Before Treatment Start	(2.b) Before Treatment Start
YYYY = TRTY	(4.a) Uncertain	(4.b) Before Treatment Start	(4.a) Uncertain	(4.c) After Treatment Start
YYYY > TRTY	(3.a) After Treatment Start	(3.b) After Treatment Start	(3.b) After Treatment Start	(3.b) After Treatment Start

1. If the CM start date year value is missing, the imputed CM start date is set to one day prior to treatment start date.
2. If the CM start date year value is less than the treatment start date year value, the CM started before treatment. Therefore:
  - a. If the CM month is missing, the imputed CM start date is set to the mid-year point (01JulYYYY).
  - b. Else if the CM month is not missing, the imputed CM start date is set to the mid-month point (15MONYYYY).
3. If the CM start date year value is greater than the treatment start date year value, the CM started after treatment. Therefore:
  - a. If the CM month is missing, the imputed CM start date is set to the year start point (01JanYYYY).
  - b. Else if the CM month is not missing, the imputed CM start date is set to the month start point (01MONYYYY).
4. If the CM start date year value is equal to the treatment start date year value:
  - a. And the CM month is missing or the CM month is equal to the treatment start date month, then the imputed CM start date is set to one day prior to treatment start date.
  - b. Else if the CM month is less than the treatment start date month, the imputed CM start date is set to the mid-month point (15MONYYYY).
  - c. Else if the CM month is greater than the treatment start date month, the imputed CM start date is set to the month start point (01MONYYYY).

If complete (imputed) CM end date is available and the imputed CM start date is greater than the (imputed) CM end date, then imputed CM start date should be set to the (imputed) CM end date.

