6.2.1.1 Permitted concomitant therapy requiring caution and/or action

No concomitant use of second line agents such as disease-modifying and/or immunosuppressive drugs will be allowed with the exception of followings:

- Systemic corticosteroid treatment ≤ 1.0 mg/kg/day (maximum 60 mg/day) in 1-2 doses of oral prednisone (or equivalent). Daily dose of systemic corticosteroid treatment (≥ 10 mg AND ≤ 1.0 mg/kg/day, maximum 60 mg/day) should be stable until Week 8. Beginning at the Week 8 visit, corticosteroid dose tapering should be attempted as per corticosteroid tapering guidelines.
- Stable dose of methotrexate (maximum of 20 mg/m²/ week) and folic/folinic acid supplementation (according to standard medical practice of the center).
- Stable dose of no more than one NSAID.

Corticosteroid tapering

Participants using concomitant corticosteroids at study entry may begin to reduce their corticosteroid dose to the lowest possible dose/discontinuation beginning at Week 8 until the End of Study. All changes in corticosteroid doses should be made in the appropriate concomitant medication eCRF.

Rules for corticosteroid tapering:

- Corticosteroid tapering is encouraged and permitted to occur beginning at Week 8 if it is the investigator's judgment that a participant's AOSD disease activity is stable and has not worsened.
- As shown in [Table 6-2](#), for oral prednisone (or equivalent) doses > 0.1 mg/kg/day, the dose should be tapered at 0.1 mg/kg of oral prednisone (or equivalent) per week. If and

when the oral prednisone (or equivalent) dose is at 0.1 mg/kg/day, the dose should be reduced to 0.05 mg/kg/day of oral prednisone (or equivalent) for 1 week, then to ≤ 0.05 mg/kg/every 48 hours for the next 2 weeks and then discontinued.

- If it is the investigator's judgment that a participant's AOSD disease activity worsens during corticosteroid tapering then the participant must return to the immediate prior dose (or higher if deemed necessary by the investigator) and may not resume corticosteroid dose tapering for at least 2 weeks.

Table 6-2 Corticosteroid tapering guideline

Prednisone (or equivalent) dose	Amount of reduction
> 0.1 mg/kg/day	Taper at 0.1 mg/kg per week until at dose of 0.1 mg/kg/day
0.1 mg/kg/day	Taper to dose of 0.05 mg/kg/day for 1 week
≤ 0.05 mg/kg/day	Alternate administration days (i.e. take dose every 48 hours) for 2 weeks and then discontinue

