## **2.5 Analysis of the primary objective**

### **2.5.1 Primary endpoint**

The primary clinical question of interest is: What is the benefit of Canakinumab in achieving clinical improvement for Japanese AOSD participants without increased use of corticosteroids regardless of study treatment discontinuations for any reason?

The justification for the primary estimand is that it will capture the actual effect of canakinumab in the condition that participants use stable dose of corticosteroids.

The primary estimand is described by the following attributes:

1. Population: Japanese AOSD participants.
2. Endpoint: Adapted ACR 30 response at Week 8
3. Treatment of interest: canakinumab 4 mg/kg s.c. (maximum of 300 mg) with stable dose of corticosteroids.

Handling of remaining intercurrent events:

1. Systemic corticosteroid dose increase and/or iv corticosteroid use before Week 8 (i.e. between baseline and Week 8 visit) for any reason: consider as non-response (Composite variable strategy)
2. Study treatment discontinuation for any reason: ignore (if adapted ACR 30 at Week 8 is available, it will be included in the analysis) (Treatment policy strategy)

The summary measure: Proportion of participants who achieve adapted ACR 30 at Week 8

The primary efficacy analysis will be based on the data up to the time when the first 11 participants in the FAS have reached Week 28 (or prematurely discontinued prior to Week 28).

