##### **Systemic corticosteroid dose increase and/or iv corticosteroid use before Week 8 for any reason**

Composite variable strategy is applied to this intercurrent event. If a participant had corticosteroid dose increase and/or iv corticosteroid use during the first 8 weeks after study treatment start, he/she will be considered as non-responder at Week 8 regardless of whether adapted ACR 30 assessment is available (non-responder imputation).

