## 5.6 Documentation of statistical methods

### 5.6.1 Calculation of prednisone equivalent dose (mg/kg/day) of oral steroids

The oral steroid dose at baseline will be the measurement on the date of baseline (Day 1) recorded on the concomitant medication page in eCRF. The oral steroid used for AOSD indication will be used. The oral steroid dose will be converted to prednisone equivalent dose using the conversion factor in [Table 5-2](#). The prednisolone equivalent dose will be derived by dividing the dose of the oral steroid dose by the corresponding conversion factor. Body weight will be the measurement at baseline (Day 1) or the last available weight before baseline.

The oral steroid dose at post-baseline assessment visits after Week 8 will be the measurement on one day before the date of corresponding assessment visits. Body weight will be the last available measurement on or before the date of steroid dose measurement.

The daily dose will be calculated by multiplying the conversion factors corresponding to the frequency recorded in eCRF (see [Table 5-3](#)). If participants use more than 2 oral steroids for AOSD on the same day, total dose per day will be used.

When a participant continued the study, if there is no concomitant oral steroid data at the assessment day, it will be considered as steroid free (0 mg).

If the oral steroid data is available but with missing information (e.g., body weight, frequency), the prednisone equivalent dose will be set to missing.

For example, if a participant weighs  $w$  kg and is taking  $x$  mg of Betamethasone 2 times per day and  $y$  mg of Hydrocortisone 3 times per day, the prednisone equivalent dose will be calculated as follows:

Prednisone equivalent dose per day =  $(x/0.12*2 + y/4*3)/w$ .

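### Uncertain corticosteroid start dates are set to the day before first dose, which can hide an early oral increase from the primary non-response rule and, in some dose bands, ease the tapering criterion

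*SAP*

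**What the plan says.** **Date rule (SAP 5.1.3.1).** When the start year equals the first-dose year, rule 4a covers two cases: "And the CM month is missing or the CM month is equal to the treatment start date month". In both, "then the imputed CM start date is set to one day prior to treatment start date". Rule 1 adds: "If the CM start date year value is missing, the imputed CM start date is set to one day prior to treatment start date". The logic matrix labels all these cells as uncertain. The same section also states: "Please note that completely missing start dates will not be imputed". No separate rule is given for corticosteroids.

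**Primary endpoint.** SAP 2.5.1 defines the intercurrent event as "Systemic corticosteroid dose increase and/or iv corticosteroid use before Week 8 (i.e. between baseline and Week 8 visit) for any reason". SAP 2.5.3 makes the participant a non-responder: "If a participant had corticosteroid dose increase and/or iv corticosteroid use during the first 8 weeks after study treatment start".

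**Shared source.** Protocol 6.2.1.1 says: "All changes in corticosteroid doses should be made in the appropriate concomitant medication eCRF". SAP 5.6.1 takes the key secondary baseline from the same page: "The oral steroid dose at baseline will be the measurement on the date of baseline (Day 1) recorded on the concomitant medication page". The tapering success criteria (Protocol 8.3.2, SAP 1.2) depend on that baseline dose.

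**The concern.** Dating an uncertain medication before treatment is harmless in a medication table. Here the same dates bear on two efficacy endpoints. A higher oral steroid dose that began after first dose, with its day or month unknown, is moved to Day -1. It then looks like background therapy and no post-baseline increase remains, so a participant who should be a non-responder can count as a responder. If the steroid is oral and given for AOSD, the raised dose also becomes the Day 1 dose, against which later tapering is judged.

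Both effects favour the drug. This runs against the plan's own approach in SAP 2.5.4, where a missing Week 8 assessment counts as non-response. The supplementary analysis in SAP 2.5.5 disregards steroid increases altogether, so it cannot reveal a misdated one. The end-date check in SAP 5.1.3.1 can only move an imputed start earlier.

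**Working it through.** The supplied documents state no power or sample-size figure to reproduce (Protocol 12.8.1 is redacted).

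**1. Which early starts are moved.** Inputs: the rules of SAP 5.1.3.1, and 56 possible start days, Day 2 to Day 57 (the Week 8 visit). First-dose dates are assumed to be spread evenly over a 365-day year.

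- Day missing only. For a first dose on day d of a D-day month, D - d later days share the month. The average is [7 × (31×30/2) + 4 × (30×29/2) + (28×27/2)] / 365 = (3255 + 1740 + 378) / 365 = 14.7 days, and 14.7/56 = 26%. The range is 0 to 30 days (0% to 54%).
- Month missing, year known. All 56 days are moved unless the window crosses into a new year. Average share moved: 1 - (56×57/2)/(365×56) = 1 - 1596/20440 = 92%, range 0% to 100%. A start in a later year goes to 1 January of that year and is not pre-dated.
- Year missing, rule 1 applied: 100%.

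These shares are conditional on a partial date existing.

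**2. Effect on the primary test.** Inputs from SAP 2.5.1 and 2.5.2: n = 11, null rate 0.40, one-sided 2.5%, normal approximation. Expected count 11 × 0.40 = 4.4; variance 11 × 0.40 × 0.60 = 2.64. z = (x - c - 4.4)/√2.64, with c = 0 or 0.5. SAP 2.5.2 specifies a continuity correction for the interval and does not say whether the test has one.

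| Responders | z, p (c = 0) | z, p (c = 0.5) |
|---|---|---|
| 7/11 | 1.60, 0.055 | 1.29, 0.098 |
| 8/11 | 2.22, 0.013 | 1.91, 0.028 |
| 9/11 | 2.83, 0.002 | 2.52, 0.006 |

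The boundary is 8/11 without correction and 9/11 with it. One hidden non-responder can carry the count across either boundary.

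The frequency of hiding is unknown. As an assumed range, suppose the true composite rate is 0.40 and hiding lifts the apparent rate by 2, 5 or 10 points. The exact chance of 8 or more responders rises from 2.9% to 4.0%, 6.1% or 11.3%. The chance of 9 or more rises from 0.6% to 0.9%, 1.5% or 3.3%.

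**3. Effect on the tapering threshold.** From Protocol 8.3.2, the Week 28 dose needed (mg/kg/day) for baseline b is:

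- b ≤ 0.2: any reduction
- b above 0.2 and up to 0.5: ≤ 0.2
- b from 0.5 to 0.8: ≤ b - 0.3
- b > 0.8: ≤ 0.5

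Invented illustration: 60 kg, first dose 7 March, 24 mg/day raised to 36 mg/day on 17 March, with the start recorded as March, day unknown. Rule 4a gives 6 March.

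- True baseline: 24/60 = 0.4, so ≤ 0.2 is needed.
- Raised record replaces the old one: 36/60 = 0.6, so ≤ 0.3 suffices.
- Records summed: 60/60 = 1.0, so ≤ 0.5 suffices. SAP 5.6.1 provides for summing more than two oral steroids, so the treatment of two overlapping records is unclear.

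The threshold does not move if true and inflated baselines both lie above 0.2 and up to 0.5, or both at 0.8 or above.

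**The case against.** **The derivation is not stated.** The SAP never says the event is read from imputed start dates. SAP 2.5.3 refers to iv use, not to its start, and SAP 2.4.2 counts medication begun before baseline and continued as concomitant. Under an overlap derivation, an iv course ending after Day 1 is still caught. A reader might infer that iv rescue is always lost; the documents do not support that. The point stands for an oral increase, because a raised dose dated to Day -1 shows no rise afterwards. An earlier-dose record ending after Day 1 would expose the discrepancy, but no rule says what to do then.

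**Partial dates may be rare.** Visits fall at Day 3, Day 15, Week 4 and Week 8 (Protocol Table 8-1). Missing values are queried (Protocol 11.2), and data for primary variables are fully verified against source (Protocol 11.3). This has real weight, though verification cannot supply a day that the source lacks. A reader might take 26% as the share of early increases lost; it is only a share of calendar days, given a partial date.

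**The flip is a boundary case.** It needs a participant with an observed ACR30 response and a count exactly at the boundary, and any one-participant error at n = 11 could do the same. That is true. The difference is that this rule errs in a known direction.

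**The tapering effect is limited.** It applies only to oral AOSD steroids and some dose bands. The key secondary endpoint has no hypothesis test (SAP 2.6.2) and also requires an ACR30 response. All of this stands.

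**Conclusion.** The point holds as a specification weakness that should be corrected. For an oral dose increase in the uncertain cells, the written rule can give a wrong result that favours the drug on the primary endpoint, and in some dose bands on the key secondary as well. For iv use it does so only under a start-date derivation, which the SAP neither adopts nor excludes. Separately, rule 1 and the matrix cell with year and month both missing contradict the statement that completely missing start dates are not imputed. That needs reconciling however often it arises.

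The size is one participant at the boundary of an 11-participant test. The 26% average assumes evenly spread first-dose dates and a missing day. A reader might infer that the primary result is already biased; the documents do not show that, because they give no count of partial steroid dates.

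**What to change.** 1. In SAP 5.1.3.1, add a rule for systemic corticosteroid records in the uncertain cells only (rules 1 and 4a). It applies where the record is iv use or a dose higher than the preceding record, and the end date and preceding record do not show a start before first dose. Impute such starts to on or after first dose, count them as the intercurrent event, and leave them out of the Day 1 baseline dose. Rules 2, 3, 4b and 4c, taper steps and the background record stay as they are. A broader rule would pull starts in a known later month back to first dose or turn taper steps into increases.
2. State in SAP 2.5.3 that iv use is identified by overlap with the baseline-to-Week 8 window.
3. Reconcile rule 1 and the matrix with the sentence on completely missing dates.
4. List every partial-date steroid record. SAP 2.14 puts the first-11 cut-off at 6 December 2022, and SAP 2.8.1.1 cites a source dated 2 October 2023, so the SAP text postdates that cut-off. If the primary rule is therefore left alone, report the conservative imputation as a sensitivity analysis.

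The cost is a few lines of text, a small programming change and queries for at most 14 participants (SAP 2.5.6). The downside is that a genuine pre-dose adjustment with an unknown day could count as non-response until queried. So could an increase after Week 8 recorded without a month.

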#### **5.1.3.2 CM end date imputation**

1. If the CM end date month is missing, the imputed end date should be set to the earliest of the ( 31DECYYYY, date of death).
2. If the CM end date day is missing, the imputed end date should be set to the earliest of the (last day of the month, date of death).
3. If CM end date year is missing or CM is ongoing, the end date will not be imputed.
4. If the imputed CM end date is less than the existing CM start date then use CM start date as CM end date.

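### Imputed oral steroid end dates are not capped at the next dose record, so a taper step with a partial end date can be read as old plus new dose

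*SAP*

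**What the plan says.** Protocol 6.2.1.1 sends steroid dose changes to the concomitant-medication form: "All changes in corticosteroid doses should be made in the appropriate concomitant medication eCRF". SAP 5.6.1 reads the baseline dose from that page on Day 1. For visits after Week 8 it takes the dose on the day before the visit. It converts each oral steroid used for AOSD to prednisone equivalents, and for several steroids on one day "total dose per day will be used". The sentence is worded for more than two steroids, but its worked example adds two (betamethasone and hydrocortisone).

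SAP 5.1.3.2 has four rules for concomitant-medication end dates:

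- Day missing: "If the CM end date day is missing, the imputed end date should be set to the earliest of the" last day of the month and the date of death.
- Month missing: "If the CM end date month is missing, the imputed end date should be set to the earliest of the" 31st of December of that year and the date of death.
- Year missing or ongoing: "If CM end date year is missing or CM is ongoing, the end date will not be imputed".
- Consistency check: "If the imputed CM end date is less than the existing CM start date then use CM start date as CM end date".

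The last rule compares dates within one record. No rule refers to another record, the visit date or the data cut-off. Under SAP 5.1.3.1, a record whose start day is missing, in a month after the treatment start month, is moved to the first of that month.

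**The concern.** A taper is a sequence of dose steps, and the guideline in Protocol Table 6-2 is weekly at first, so several steps can fall in one month. If each step is a new record, an extended end date leaves the old record open after its replacement has started. Two doses are then active on one day, and the only rule given for concurrent oral steroids is to total them. The derived dose becomes old plus new. If the step was to zero, the old dose persists instead of the 0 mg that SAP 5.6.1 assigns when no steroid is recorded.

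The outputs at stake are the Week 28 tapering endpoint with its tapered and steroid-free classes (SAP 2.6.2), oral steroid dose by visit (SAP 2.7.2), and the table of doses tapered below 5 mg/day (SAP 2.14).

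**Working it through.** The plan states no figure on this point, so there is none to reproduce. The check applies SAP 5.1.3.2 and 5.6.1 literally to short tapers and scores the dose part of the success criteria (SAP 1.2), assuming the adapted ACR30 condition is met. Doses without a unit are in mg/kg/day.

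**One step, 60 kg (illustrative).** 12 mg/day truly ends 10 June but is recorded as June with the day missing; 9 mg/day starts 11 June; the dose is read on 20 June. The old record is extended to 30 June.

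- True dose: 9/60 = 0.15.
- Derived dose: (12 + 9)/60 = 0.35.

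The true dose meets the criterion of 0.2 or less at any baseline. For the derived 0.35:

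- Baseline above 0.8: at most 0.5 is needed, so it still passes.
- Baseline 0.65 to 0.8: the reduction is at least 0.65 − 0.35 = 0.3, so it still passes.
- Baseline 0.5 to below 0.65: the reduction is under 0.3, so it fails.
- Baseline 0.4, or anything else below 0.5: it fails.

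**Other steps, reading date inside the overlap.** All are true successes.

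| Baseline | Step | Derived | Scored as |
|---|---|---|---|
| 0.4 | 0.3 to 0.2 | 0.5 (above baseline) | failure |
| 0.4 | 0.2 to 0.1 | 0.3 | failure |
| 0.6 | 0.4 to 0.3 | 0.7 (above baseline) | failure |
| 0.9 | 0.5 to 0.4 | 0.9 (equals baseline) | failure |
| 0.9 | 0.3 to 0.2 | 0.5 | success |
| 0.4 | 0.4 to 0 | 0.4 | failure |
| 0.4 | 0.2 to 0 | 0.2 | success, but not steroid free |

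**Several steps in one month.** With 0.4, 0.3, 0.2, 0.1 and 0.05 in weekly sequence and every end day missing, the last step reads 0.4 + 0.3 + 0.2 + 0.1 + 0.05 = 1.05 against a true 0.05. With each imputed end date capped at the day before the next start, the derived dose equals the true dose on every day checked.

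**Chance of overlap, given a partial end date.** Assume the old record truly ended 1 to 28 days before the reading date, uniformly (mean 14.5 days).

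- Day missing: about 1 − 14.5/30.4 = 52%.
- Month missing: about 1 − 14.5/365 = 96%.
- Alternative assumption, step day and reading date uniform in the same 30-day month: 435/900 = 48%.

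With the month missing, a step on 10 June stays open for 204 days, and 204/28 is about 7 four-weekly visits.

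**Effect of one participant.** 1/14 = 7.1 points and 1/11 = 9.1 points. The denominator can be smaller than the FAS (SAP 2.6.2), which would make the shift larger.

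**Opposite direction at Day 1.** If a 0.5 record that ended before Day 1 is extended past it while 0.4 is current, baseline reads 0.9, and an unchanged 0.4 then passes as 0.5 or less. This requires the old record to be handled as concomitant: SAP 5.1.3.3 imputes no dates for prior therapy, and the SAP does not say how a partial end date in the Day 1 month is classified.

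**The case against.** Much of the opposing case stands.

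- **Inferred steps.** That each dose step is a new record is the usual form of dated dose data, but it is not stated. Totalling two records of the same drug is also inferred, since the worked example adds two different drugs. Still, no other rule for overlapping records is given.
- **Another rule might apply.** SAP 5.6.1 sets the dose to missing when steroid data lack information, with weight and frequency as open-ended examples, and SAP 2.6.3 then carries the last value forward. A partial date could be read into that list. But SAP 5.1.3.2 completes such dates, after which nothing is missing, so neither rule clearly rescues the dose.
- **Upstream control.** Protocol 11.2 provides for queries on missing values, so partial steroid dates may be few or absent.
- **Timing.** An uninterrupted guideline taper from 1.0 mg/kg/day started at Week 8 takes 9 weekly steps to 0.1, then 1 week, then 2 weeks, so it ends at about Week 8 + 12 = 20. A missing-day overlap would then be over before Week 28. Slower, later or interrupted tapers, and missing months, remain exposed, as do earlier visits in the by-visit tables.
- **Limited consequence.** The key secondary analysis is a frequency table without a hypothesis test.

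A reader might infer that an overlap before Week 8 would be scored as non-response on the primary endpoint. The documents do not support that. The dose algorithm covers Day 1 and visits after Week 8, SAP 2.5.3 does not route the dose-increase event through it, and the dose should be stable until Week 8.

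**Conclusion.** The gap is real and worth closing. Followed literally, SAP 5.1.3.2 and 5.6.1 can give a wrong steroid dose for the Week 28 tapering endpoint and the steroid-dose tables. This rests on four assumptions: a step is a new record, the old record's end date is partial, the reading date falls between the true and the imputed stop, and concurrent records are totalled. Whether the result changes depends on the baseline dose and the step; some participants still pass.

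Two further readings go too far. The error does not always show a taper as an increase from baseline: the derived dose exceeds the previous step whenever the new dose is above zero, but it may stay below baseline, and a stop to zero shows as no change. The 52% and 96% are conditional on a partial end date and a recent step; they are not risks for the endpoint. Nor is the rule safely conservative, because an overlap at Day 1 could favour success.

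The realised effect may be zero, because the documents do not give the number of partial steroid end dates.

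**What to change.** Add to SAP 5.1.3.2, for oral steroid records for AOSD: an imputed end date is the earliest of month or year end, death, the last visit or data cut-off, and the day before the start of the next oral steroid record that replaces it. This applies to the same drug or a switch of drug, unless the eCRF shows that the records were taken together.

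Where the old end date and the new start date are both partial, query the site. If that does not resolve it, apply one stated rule, for example counting only the later record from its imputed start. In a taper that choice can bring the lower dose forward to the first of the month, so list the affected participants beside the tapering table. Also state in SAP 5.6.1 whether a partial date ever triggers the set-to-missing rule, and correct the wording so that it covers two steroids, as the example does.

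The cost is a few SAP sentences and a few lines of programming. No new data collection is needed beyond queries on any partial steroid dates.
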